### Objective Response Rate (ORR)

Objective response rate is defined as the proportion of subjects whose BOR is one of the following responses divided by the number of treated subjects or number of randomized subjects in nivolumab/daratumumab cohort.

- for lymphoma subjects whose BOR is either complete remission or partial remission
- for myeloma subjects whose BOR is stringent complete response, complete response, very good partial response, or partial response

### Duration of Response

Duration of response will be only calculated for subjects with best overall response of objective response defined as above. The duration of response is defined as the time between the date of first documented objective response and the date of first documented disease progression, or death, whichever is earlier. Subjects who remain alive and have not progressed will be censored on the last adequate efficacy assessment date prior to subsequent cancer therapy. Allogeneic SCT and ASCT will be considered as subsequent therapy.

Sensitivity analyses will be performed based on an alternate censoring scheme (same as PFS censoring scheme) to account for non-uniform and infrequent tumor assessment schedules. For this analysis, subjects will be censored on their last visit date, defined as the last date of dosing, tumor assessment or lab assessment, whichever occurs last.

Duration of response will be evaluated for responders (PR or CR for lymphoma subjects; SCR, CR, VGPR, or PR for myeloma subjects) only.

### **Time to Response (TTR)**

Time to response is defined as the time from date of first dose of study medication or date of randomization for nivolumab/daratumumab to the date of the first documented objective response. Time to response will only be evaluated in subjects with minimal objective response of PR.

Time to best response is defined as the time from date of first dose of study medication or date of randomization for nivolumab/daratumumab to the date of the best overall response.

### **Tumor Measurements (Lymphoma)**

For Hodgkin/PMBL, T cell lymphoma, B cell lymphoma subjects, target lesion tumor burden will be derived from tumor measurements.

### **Serum and Urine M-Protein and Free Light Chain (Myeloma)**

Serum and urine tests will be performed for Myeloma subjects. For the complete list of the serum and urine tests, please refer to section 5.1 of the protocol.

### **FDG-PET Assessment (HL or PMBL)**

FDG-PET/CT imaging scans were performed at screening, and the end of treatment for HL or PMBL subjects. The FDG-PET endpoints are the overall assessment of the scan.

### **mSWAT (cutaneous T cell lymphoma)**

Response in skin for subjects with cutaneous T cell lymphoma will be evaluated by the mSWAT score which is reported by investigators.

### **Minimal Residual Disease (MRD)**

In the nivolumab/daratumumab cohorts, MRD from bone marrow aspirate will be evaluated. MRD will be assessed by Next Generational Flow Cytometry (NGF) and Next Generational Sequencing (NGS).

The timepoint MRD negativity status is a dichotomized variable for quantifiable MRD detection. MRD negativity status will be considered at  $10^{-5}$ , as per IMWG guidelines; other sensitivity levels such as  $10^{-4}$  and  $10^{-6}$  will also be considered.

The first MRD negative status is defined as the first negative status designation over the study as a whole, recorded between the date of first dose and the date of objectively documented progression or the date of subsequent therapy, whichever occurs first.

The best MRD negative status is defined as the best status designation with the lowest sensitivity level over the study as a whole, recorded between the date of first dose and the date of objectively documented progression or the date of subsequent therapy, whichever occurs first.

Time to the first MRD negative status is defined as the time from the date of randomization to the date of the first MRD negative status.

The duration of the MRD negativity is defined as the time between the date of first MRD negativity to the date of the first MRD positivity, or the date of the first objectively documented progression as assessed according to IMWG criteria or death due to any cause whichever is earlier prior to the initiation of subsequent anti-cancer therapy. Subjects who didn't have MRD positivity, and didn't progress nor die will be censored on the date of their last MRD negativity prior to the initiation of subsequent anti-cancer therapy.

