Bone marrow and peripheral blood samples are also needed to better understand how the immune microenvironment may contribute to immune evasion, the progression of multiple myeloma, and potential synergies between nivolumab and daratumumab. Bone marrow from every harvest should also be submitted for biomarker analysis, as described in [Table 5.1-6](#). At the time of the scheduled bone marrow aspirate, the PI will determine if there have been significant changes in the clinical course to suggest that subjects can no longer undergo the procedure safely. Similarly, the PI will determine if there have been significant changes in the clinical course to suggest that subjects can no longer safely undergo the additional peripheral blood collection for biomarkers assessments. These subjects may continue therapy.

Clinical response will be assessed based on the modified IMWG criteria based on serum and urine laboratory assessments every 4 weeks from Cycle 1 Day 1 until disease progression,

irrespective of dose delays or treatment interruptions. All response (\geq PR) and progression categories require 2 consecutive laboratory assessments to confirm response or progression before initiation of any new therapy. If progression is confirmed at the second laboratory assessment, all study treatment will be discontinued.

To assess potential daratumumab and nivolumab interference with serum M protein quantification, samples may be analyzed to distinguish daratumumab and nivolumab from endogenous myeloma protein (M protein).

Subjects who experience AEs that require discontinuation of daratumumab may be allowed to continue therapy with nivolumab (if randomized to the ND arm), with or without pomalidomide and dexamethasone, (if randomized to the NDPd arm) if deemed in their best interest by both the PI and the BMS medical monitor. Subjects must be deriving clinical benefit.

Subjects who experience AEs that require discontinuation of nivolumab may be allowed to continue therapy with daratumumab (if randomized to ND arm), with or without pomalidomide and dexamethasone, (if randomized to NDPd arm), if deemed in their best interest by both the PI and the BMS medical monitor. Subjects must be deriving clinical benefit.

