4.1.5 Dose Delay, Interruption, or Discontinuation

If the dose of nivolumab, daratumumab, pomalidomide and/or dexamethasone is interrupted or discontinued, the treatment with the other drugs may continue as scheduled if deemed in their

best interest by both the PI and the BMS medical monitor. Subjects must be deriving clinical benefit.

Each cycle is 28 days. While dose delays (within the allowed window determined below for nivolumab and daratumumab) or interruptions are permitted, the start of each cycle cannot be delayed and is fixed (ie, anchored) relative to Cycle 1 Day 1. Adjustments to the Cycle 1 Day 1 anchored schedule should not be performed. Should the start of a cycle be delayed, it is expected the following cycle begin as anchored to Cycle 1 Day 1. Delayed doses which fall outside of the allowed window for delay for the respective cycle should be skipped. Subjects may continue on study therapy even if components of the study therapy must be discontinued.

Please consult the BMS Medical Monitor or any questions regarding dose interruption or study therapy discontinuation.

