5.4.1.1 Primary Efficacy Assessment: MRD

Molecular minimum residual disease (MRD) assessment will be performed via the Adaptive® ClonoSIGHT assay and bone marrow aspirate samples are required at the following time points:

- Bone marrow aspirate samples at Screening, Day 1 Cycle 4 or at the time of VGPR or better, whichever occurs first, and every 6 cycles thereafter until disease progression. In subjects with confirmed PD prior to Day 1 Cycle 4, bone marrow aspirate will be performed upon confirmation of PD. If bone marrow aspirate was inadvertently not collected or unable to be collected at these required time points, the study medical Monitor should be contacted to discuss the timing of the collection

Cytometry MRD from bone marrow aspirates will be done at the same time points as for molecular MRD, except for the Screening timepoint.

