### **MRD (nivolumab-daratumumab)**

Analyses of MRD status will be based on all evaluable MRD subjects and performed at each sensitivity level. Both molecular and cytometry MRD status from bone marrow aspirate will be evaluated. MRD negativity status will be evaluated by timepoints. Summary statistics of time to the first MRD negativity will be provided by treatment group for subjects achieving MRD negative status. Cumulative MRD negativity rates will be tabulated at the first on-study assessment (i.e, C4D1 or  $\geq$ VGPR, whichever occurs first) and every 6 months thereafter depending on the data availability. Median duration of the MRD negativity and corresponding two-sided 95% CI will be analyzed by KM product limit method for subjects who achieved MRD negative status depending on the data availability. A plot of individual time course of abnormal bone marrow plasma cells will be produced.

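### Duration of MRD negativity: censoring at the last negative marrow, while progression and death count between marrows, biases the Kaplan-Meier curve low for the endpoint as the SAP defines it

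*SAP*

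**What the plan says.** SAP 4.2.2, under Minimal Residual Disease, starts the clock at first MRD negativity. A marrow that turns positive stops it. Progression and death stop it too, in these words: "or the date of the first objectively documented progression as assessed according to IMWG criteria or death due to any cause whichever is earlier". All of these count only before any subsequent therapy. A subject with none of these "will be censored on the date of their last MRD negativity prior to the initiation of subsequent anti-cancer therapy".

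The two kinds of event are looked for on different schedules:

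- **Marrow.** Protocol 5.4.1.1 takes aspirates at "Day 1 Cycle 4 or at the time of VGPR or better, whichever occurs first, and every 6 cycles thereafter until disease progression". Protocol 4.1.5 states "Each cycle is 28 days". Protocol 5.4.2 lets the investigator forgo a marrow judged unsafe, so the gap can be longer, and it makes a marrow at progression optional.
- **Progression.** Protocol 3.1 requires "serum and urine laboratory assessments every 4 weeks from Cycle 1 Day 1 until disease progression".

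SAP 7.5 gives the analysis: "Median duration of the MRD negativity and corresponding two-sided 95% CI will be analyzed by KM product limit method", among subjects who reached negativity and depending on data availability. SAP 4.2.2 adds last-visit sensitivity censoring for PFS and for duration of response. Duration of MRD negativity has no such sensitivity analysis.

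**The concern.** Kaplan-Meier assumes that censoring carries no information about the event. Here, whether the weeks after the last marrow count depends on how they ended. If they ended in progression or death, they count as time at risk with an event at the end. If they ended without an event, they are discarded. Event-free time leaves the risk set and event time stays in, so the estimated hazard is too high.

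The reported median and the curve would then describe loss of negativity as faster than was documented. Early data cuts are the most exposed. The final analysis needs only 3 months of minimum follow-up (Protocol 8.4.2), and the Cohort B interim needs 3 months in half of each arm (Protocol 8.5.1). Cycle 4 Day 1 falls 3 × 28 = 84 days after Cycle 1 Day 1, so some negative subjects may have one on-study marrow only and would contribute zero duration.

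**Working it through.** The plan gives no figure for this endpoint, so there is none to reproduce.

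**1. Schedule.** 6 cycles × 28 days = 168 days = 24 weeks between marrows. 168 / 28 = 6 disease assessments fall in each marrow interval.

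**2. Smallest example.** Two subjects have their first negative marrow on day 0 and are followed to day 140. One progresses on day 140 and the other is event-free at that assessment.

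- SAP rule: the event-free subject is censored on day 0. One subject is at risk on day 140, so S(140) = 1 − 1/1 = 0.
- Censoring at the last disease assessment: two are at risk, so S(140) = 1 − 1/2 = 0.5, which is what happened.

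**3. Assumed hazards (not in the documents).** Progression or death is exponential with median 540 days and seen on a 28-day grid. Marrow relapse is exponential with median 720 days, independent, and seen at 168-day marrows. Progression or death is then (1/540) / (1/540 + 1/720) = 57% of the hazard. The documented endpoint has a closed form:

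- Day 308: 2^(−308/540) × 2^(−168/720) = 0.673 × 0.851 = 57%
- Day 336: 2^(−336/540) × 2^(−336/720) = 0.650 × 0.724 = 47%

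The curve drops through 50% at the day-336 marrow, so the true median is 336 days.

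**4. SAP rule under these hazards**, by simulation of 400,000 subjects per scenario, varying only follow-up after first negativity (uniform):

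| Follow-up (days) | SAP rule at day 336 | Truth | Shortfall | SAP median |
|---|---|---|---|---|
| 28–365 | 29–30% | 47% | about 17 points | 224 days |
| 28–730 | about 44% | 47% | about 3 points | 336 days |
| 90–730 | 44.5% | 47% | about 2.5 points | 336 days |
| 0–1,095 | about 45.5% | 47% | about 1.5 points | 336 days |
| 180–900 | about 46% | 47% | about 1 point | 336 days |

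In the first row 37% of negative subjects are censored on day 0. With 8 such subjects (the plan's 20% of 40) that is 0.37 × 8 ≈ 3. Censoring at the last 28-day assessment recovers the true value to about 0.1 points in every row.

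**5. Other assumed hazards.** The overall median to true loss, progression or death is 12 to 24 months, progression or death is 25–75% of the hazard, and progression is dated when it occurs.

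| Follow-up (months) | Shortfall in the curve | Shortfall in the median |
|---|---|---|
| 0–12 | 2.8 to 10.3 points at 6 months | – |
| 0–24 | 1.3 to 5.0 points at 12 months | 1.4 to 6.1 months |
| 0–36 | 0.7 to 2.7 points at 12 months | 1.1 to 3.3 months |

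The unchanged median in step 4 therefore owes something to the 10-point drop at day 336 (57% to 47%) and is not general. In the 0–24 month scenarios, censoring at the last 4-weekly assessment is within 0.1 to 0.8 points at 12 months.

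**6. Control.** With progression and death set to 0% of the hazard, the SAP rule is unbiased (12-month value 65.4% both ways; overall median 18 months, follow-up 0–24 months). The whole effect comes from progression and death counted between marrows.

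**7. Against biological loss.** In the step-3 model the true chance of still being negative and event-free at day 252 is 2^(−252/540) × 2^(−252/720) = 0.724 × 0.785 = 57%. The documented value is 0.724 × 2^(−168/720) = 0.724 × 0.851 = 62%. With 90–730 days of follow-up the SAP rule gives 59%.

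**The case against.** The strongest reply accepts the mechanism and disputes the size, the target and the importance.

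- **Size.** A reader might infer a bias of 17 points and 336 − 224 = 112 days in the median. That needs every negative subject to have at most 365 days after first negativity, and the documents do not support such a cap. SAP 4.2.2 plans PFS rates out to 24 months, treatment runs until progression, and Cohort A closed to enrolment under Revised Protocol 14 in February 2018. The hazards are assumed too. If progression follows MRD loss after a median lag of 180 to 365 days, the 336-day shortfall is about 0.6 to 1.7 points with 90–730 days of follow-up and about 7 to 14 points with short follow-up. This stands: direction is secure, size is not.
- **Target.** A reader might also infer that time truly MRD-negative is understated. That does not follow. Late detection at 168-day marrows pushes the other way, and in step 7 the SAP rule lies closer to the biological value than the documented curve does. Censoring at the last marrow is also sound if MRD positivity is the only event. This stands as a limit on wording. It does not rescue the rule for the composite endpoint the SAP defines.
- **Importance.** The secondary objective is MRD status. Duration of negativity is absent from the MRD text in Protocol 8.3.2.1 and 8.4.2. Cohort B is not powered for testing. At the planning rates there are 0.30 × 20 = 6 and 0.20 × 40 = 8 negative subjects per arm. With 8 subjects the binomial standard error at 62% is √(0.62 × 0.38 / 8) = 17 points. Timepoint status and cumulative negativity rates do not use this rule, and the Kaplan-Meier analysis may be omitted when data are thin. This stands and keeps the severity low. It is no reason to retain an avoidable bias.

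**Conclusion.** The point holds for the endpoint as the SAP defines it. Whenever some events are progression or death between marrows, censoring is informative and the Kaplan-Meier curve is biased low relative to first documented loss of MRD negativity.

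Under the 540- and 720-day assumptions the 336-day estimate is about 17 points low with at most one year of follow-up after first negativity. It is about 1 to 3 points low, with the median unchanged, once follow-up extends to about two years or more. Other plausible hazards leave the median 1.1 to 6.1 months short at two to three years of maximum follow-up. None of these figures can be fixed from the documents. Nothing is claimed about biological duration.

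This is a low-severity recommendation for a descriptive analysis, and it matters most at an early data cut.

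**What to change.** In SAP 4.2.2, under Minimal Residual Disease:

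- Censor subjects without MRD positivity, progression or death at the last adequate IMWG disease assessment on or before subsequent therapy. The SAP already defines an adequate assessment for myeloma subjects in its PFS text.
- Leave event dates as they are, and label the endpoint time to first documented loss of MRD negativity.
- Report the present last-negative-marrow rule as a sensitivity analysis.

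The cost is a sentence or two in the SAP and no new data. The downside is that up to 24 weeks, or more if a marrow is missed, are credited as negative without a marrow. The SAP already does this for subjects whose next marrow turns positive, and the new label makes it explicit.

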#### **4.2.3 Immunogenicity**

The immunogenicity status of nivolumab, ipilimumab, and lirilumab will be analyzed.

Refer to Core Safety SAP.

[REDACTED]

CSR.

[REDACTED]

## 5 SAMPLE SIZE AND POWER

### NIVOLUMAB MONOTHERAPY COHORTS

The sample size in the escalation phase is not based on statistical consideration, but rather depends on the number of observed toxicities; between 6 and 9 subjects are expected to be treated at each dose. At the dose expansion cohorts, approximately 23 subjects are expected to be enrolled in each of four tumor types and treated at the previously determined MTD or if no MTD is identified a maximum dose of 3 mg/kg.

In an expansion cohort, if 4 (17.4%) or 5 (21.7%) responses are observed with 23 subjects in each cohort, then the lower limit of the 90% one-sided confidence intervals for the objective response rate would be 7.8% and 11.0% respectively. These calculations are based on the Clopper-Pearson method for exact confidence intervals.

In addition, if the true ORR in a tumor type/expansion cohort is 20% then with 23 patients in each cohort there is 86.7% chance of observing at least 3 responses or 13.3% chance of observing 0, 1 or 2 responses (false negative rate). If the true ORR in a tumor type is 5% rather than 20%, then there is 10.5% chance that there will be at least 3 responses in 23 subjects (false positive rate).

### IPILIMUMAB/NIVOLUMAB COHORTS

In a tumor cohort, if 3 (21%) or 4 (29%) responses are observed with 14 subjects in each cohort, then the lower limit of the 90% one-sided confidence intervals for the objective response rate would be 8% and 13% respectively. These calculations are based on the Clopper-Pearson method for exact confidence intervals.

In addition, if the true ORR in a tumor cohort is 20% then with 14 patients in each cohort there is 80% chance of observing at least 2 responses and 96% chance of observing at least 1 response, or 20% chance of observing 0 or 1 response (false negative rate) and 4% chance of observing 0 response (false negative rate). If the true ORR in a tumor cohort is 5% rather than 20%, then there is 15% chance that there will be at least 2 responses in 14 subjects (false positive rate).

The sample size in the exploratory schedule evaluation is not based on statistical considerations, but rather depends on the number of observed toxicities; between 3 and 9 subjects are expected to be treated in cohorts 3 and 4.

Subsequent cohorts may be tested if required.

Administration of the study drug to 9 subjects at a dose level in exploratory schedule evaluation provides 90% probability of observing at least one occurrence of any adverse event that would occur with a 22% incidence in the population from which the sample is drawn.

Approximately 6-18 subjects are expected to be enrolled in exploratory schedule evaluation and approximately 56 in tumor expansion.

## LIRILUMAB/NIVOLUMAB COHORTS

In a tumor cohort, if 4 (20%) or 5 (25%) responses are observed with 20 subjects in each cohort, then the lower limit of the 90% one-sided confidence intervals for the objective response rate would be 9% and 13% respectively. In a tumor cohort, if 3 (10%) or 6 (20%) responses are observed with 30 subjects in each cohort, then the lower limit of the 90% one-sided confidence intervals for the objective response rate would be 4% and 11% respectively. These calculations are based on the Clopper-Pearson method for exact confidence intervals.

In addition, if the true ORR in a tumor cohorts is 20% then with 20 patients in each cohort there is 93% chance of observing at least 2 responses, or 7% chance of observing 0 or 1 response (false negative rate). If the true ORR in a tumor type is 5% rather than 20%, then there is 26% chance that there will be at least 2 responses in 20 subjects (false positive rate). If the true ORR in a tumor cohort is 20% then with 30 patients in each cohort there is 88% chance of observing at least 4 responses, or 12% chance of observing 3 or fewer responses (false negative rate).

If the true ORR in a tumor type is 5% rather than 20%, then there is 6% chance that there will be at least 4 responses in 30 subjects (false positive rate).

Approximately 130 subjects are expected to be enrolled in tumor cohorts.

The probability (%) of observing at least a certain response rate given a true ORR (%) is presented in Table 8.1-1 of the protocol.

## NIVOLUMAB/DARATUMUMAB COHORTS

Cohort A (ND ± Pd) is closed to enrollment.

The planned sample size for Cohort B (ND, D) will be approximately 60 treated subjects, randomized in a 2:1 ratio to the ND and D arms, respectively. The sample size is not powered for statistical hypothesis testing, but designed to evaluate both the safety profile and clinical benefit of nivolumab in combination with daratumumab.

If the true toxicities incidence rate in a cohort is 20% then with 20 patients in the D cohort there is a 7% chance of observing 0 - 1 toxicities (false negative rate). If the true toxicities incidence rate in a cohort is 5% rather than 20%, then there is 26% chance that there will be at least 2 toxicities in 20 subjects (false positive rate). If the true toxicities incidence rate in a cohort is 20% then with 40 patients in ND cohort there is 3% chance of observing 0 - 3 toxicities (false negative rate). If the true toxicities incidence rate in a cohort is 5% rather than 20%, then there is 14% chance that there will be at least 4 toxicities in 40 subjects (false positive rate).

In two daratumumab monotherapy studies in relapsed/refractory MM patients, including a Phase 1/2 dose escalation study (GEN501) in patients with at least 2 lines of prior therapy and a Phase 2 study (SIRIUS) in patients with at least 3 lines of prior therapy, the ORR were 36% and 29.2% respectively. In two combination studies in relapsed/refractory MM patients with at least 2 lines of prior therapy, including a Phase 1b study of daratumumab in combination with pomalidomide and dexamethasone and a Phase 1 dose-escalation study of pembrolizumab in combination with pomalidomide and dexamethasone, the ORR were 60%. At observed ORR  $\geq$

55% with 20 subjects, the lower bound of the 95% CI exceeds 31.5%. At observed ORR  $\geq 77.5\%$  with 40 subjects, the lower bound of the 95% CI exceeds 61.5%.

At observed MRD negative rate  $\geq 30\%$  with 20 subjects and observed MRD-target negativity rates  $\geq 20\%$  with 40 subjects, the lower bound of the 95% CI are 11.9% and 9.1% respectively, compares favorably to historical MRD-target negativity rate of 8% in the target population.

